1. UPDATE HISTORY

Date	Summary
02/20/2023	Initial protocol completed
04/19/2023	Offer in-person consenting, meditation, and nutrition group classes
06/15/2023	Add the Brief Capacity Assessment Questionnaire
08/04/2023	Add cardiovascular procedures to the inclusion criteria
09/06/2023	Update the screening procedure by removing the high-risk feature requirement and increasing the age to 70 for email screening. Surgeons can directly refer their patients to the study team (including patients aged 65-69 years) if they feel these patients are high-risk based on their clinical judgement.

2. OVERVIEW

The purpose of this feasibility pilot study is to understand how a prehabilitation program for older adults with frailty can best be optimized to prepare at-risk patients for major surgery. As such, our program interventions target major risk factors that are modifiable yet rarely addressed in the pre-surgery period (physical function, nutrition, pain, sleep, anxiety, and cognition). We also aim to determine how these interventions can best be delivered for optimal participation.

Participants will receive 3 to 4 weeks of exercise training with a physical therapist, nutrition education with a registered dietitian, meditation with an experienced meditation teacher, and cognitive behavioral intervention to discuss goals, facilitators and barriers to program adherence with the goal to enhance motivation and promote self-efficacy. Two (2) follow-up assessments will additionally be performed at days 30 and 90. Further details of the intervention are provided below:

- Exercise training with home/virtual/in-center physical therapy will take place on average twice a week for 1 hour per session over 3-4 weeks. The participant will be encouraged to exercise on their own for 30 minutes per day for 4 or more days a week and track exercise in a diary (number of minutes achieved per day). They will also be asked to wear a physical activity tracking device (Fitbit Fitness tracker) to measure daily number of steps, active minutes, and heart rate. This device will also remind the participant to get up and move throughout the day.
- Nutrition class with a licensed nutritionist (registered dietitian) will take place on average once a week for 1 hour per session over 3-4 weeks. The participant will also be asked to drink/consume 1 high calorie, high protein nutritional supplement per day which will be provided to them by the study. They will be asked to write down their approximate daily food intake in a diary (3 days/week) – this will be an informal accounting of their intake with the primary focus being on protein-containing food items. This information will be used to measure their protein intake during their participation in the study.
- Meditation with a yoga/meditation teacher will take place once a week for 1 hour per session over 3-4 weeks. The participant will also be asked to practice meditation on their own for at least 12 minutes each day and track in a diary (number of minutes achieved each day).
- Weekly check-in calls will take place once a week for about 30 minutes per session over 3-4 weeks. During these calls the participant will talk about their goals, discuss personal motivation, and review their progress. They will be asked about any potential adverse events (such as sore muscles or falls).
- A 30 minute telephone interview will take place at the end of the intervention (in weeks 3 or 4). The participant will be asked to provide feedback discussing what parts of the

intervention worked well and what did not. We will use this information for protocol refinement.

The primary outcome is the feasibility of the prehabilitation protocol, defined as the proportion of patients to whom we can deliver an adequate dose ($\geq 50\%$ of the planned sessions) of the 3 core interventions: physical therapy ($\geq 4/8$ sessions), nutrition ($\geq 2/4$ sessions), and meditation ($\geq 2/4$ sessions). Secondary outcomes include 1) adherence to exercise, protein intake and meditation; 2) changes in 5-chair stand time, dominant handgrip strength, patient-centered outcomes, measured using PROMIS scores in physical function, cognitive function, participation in social roles/activities, depression, anxiety, sleep disturbance, pain and fatigue domains at baseline, following completion of the prehabilitation (before surgery), and on postoperative days 30 and 90; 3) clinical outcomes (3-D Confusion Assessment Method,¹ a composite complication score,² length of stay, and 30-day readmission and death); and 4) Postoperative Quality of Recovery Scale³ to be obtained around postoperative day 3; 5) adverse events.

The proposed research will provide necessary information for a larger randomized controlled trial (RCT).

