5. STUDY POPULATION

We will review schedules to identify patients who meet the following inclusion (5.1) and exclusion criteria (5.2). A trained research assistant will perform preoperative geriatric assessment—which consists of 1) medical history (automated in EHR), 2) self-reported functional status (a questionnaire of 22 daily activities and physical tasks), 3) tests of cognitive function (Mini-Cog or MoCA test) and physical function (gait speed, chair stands, and grip strength), and 4) nutritional status (automated in EHR)—and calculate a frailty index using our EHR calculator. For eligible patients, we will explain the purpose of our study to the patients and their surgeon and ask whether they are willing to participate in 3 to 4 weeks of prehabilitation. Remote or e-consent will be obtained. Screening of potential participants will take place during the surgeon’s office visit. The assessment of eligibility will take place by telephone. Our target enrollment is 30 patients (2 patients per week for 15 weeks). See the detailed inclusion and exclusion criteria provided below:

5.1 Inclusion Criteria:

- Patient is ≥ 70 years
- Patient is ≥ 65 years old AND high risks per surgeon’s clinical judgement
- Patient is scheduled to have a gastrointestinal, gynecological oncologic, urologic, and cardiovascular procedure
- Patient provides an informed e-consent or remote consent

5.2 Exclusion Criteria:

- Surgery is scheduled less than 21 days from the expected start date of the prehabilitation intervention
- Patient is considered an inappropriate candidate per the surgeon’s assessment.
- Non-English speaking
- Patient has a major cognitive impairment, which will be defined as telephone Montreal Cognitive Assessment (MoCA) <18 or Brief Capacity Assessment Questionnaire
- Patients with chronic kidney disease stage 3 or higher will be excluded from receiving protein supplement of the prehabilitation intervention.

[figure not shown]

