6.1 Baseline Assessment

Once informed e-consent or remote consent is signed, trained research personnel will administer additional measurements that are not collected as part of preoperative assessment. These measurements (provided below) may be conducted 1) during the telephone call during which informed consent is obtained; 2) during a separate call (if

requested by the patient or caregiver); 3) email survey; 4) during an in-person physical therapy session (for gait speed, chair stands, and handgrip strength); or 5) a combination of these modalities.

- Usual walking speed from 4-meter walk (if not already measured)
- Time to complete 5 chair stands (if not already measured)
- Dominant handgrip strength: average of 3 measurements (if not already measured)
- 3-day diet recall (done by telephone)
- PROMIS Profile CAT v1.0 is a 29-item, computer adaptive, patient-reported outcome measure of social roles/activities, anxiety, depression, fatigue, pain interference/intensity, physical function, and sleep disturbance domains (may be done by telephone or email)
- PROMIS v2.0 Cognition CAT is a 12-item, computer adaptive, patient-reported outcome measure of cognitive function domain (may be done by telephone)

PROMIS (available at <https://www.healthmeasures.net/index.php>) is a publicly available, validated system of highly reliable, precise measures of patient-reported health status for physical, mental, and social well-being for general population as well as people with chronic conditions. It is designed to enhance communications between clinicians and patients in diverse clinical and research settings. Computer adaptive test (CAT) allows accurate assessment with a limited number of questions from the PROMIS item bank, thereby reducing participant burden.

6.2 Medical Record Review:

Trained research personnel will obtain the following data from the OMR and record them in REDCap database:

- Demographic information: age, sex, race, ethnicity
- Chronic comorbidities
- Self-reported functional status: ADL, IADL, physical tasks by Nagi and Rosow-Breslau
- Cognitive function: telephone MOCA
- Physical function: gait speed, dominant handgrip strength, and chair stands
- Nutritional status: height, weight, BMI, weight loss in the past year, serum albumin level

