8.2 Secondary Outcomes

For *secondary outcomes*, we will measure the following:

- Change in 5-chair stand test (time)
 - Measurement: time to complete 5 chair stands (seconds), post-prehabilitation minus pre-prehabilitation
 - Range: -60 to 60 seconds (higher values indicate worsening performance)
- Change in dominant handgrip strength (kg)
 - Measurement: average of 3 measurements of dominant handgrip strength, post-prehabilitation minus pre-prehabilitation
 - Range: -50 to 50 kg (higher values indicate improved performance)
- Change in protein intake (grams)
 - Measurement: 3-day average protein intake from dietary recall, post-prehabilitation minus pre-prehabilitation
 - Range: -100 to 100 grams (higher values indicate greater intake)
- Adherence to exercise
 - Measurement: proportion of days with ≥ 30 minutes of exercise out of 21-28 days per self-report
 - Range: 0-100% (higher values indicate better adherence)
- Adherence to protein intake
 - Measurement: proportion of oral nutritional supplement consumed over the total number of supplements provided per self-report

- Range: 0-100% (higher values indicate better adherence)
- Adherence to meditation
 - Measurement: proportion of days with ≥ 12 minutes of meditation out of 21-28 days per self-report
 - Range: 0-100% (higher values indicate better adherence)
- Adverse events
 - Measurement: proportion of patients who experience any adverse events per self-report
 - Range: 0-100% (higher values indicate more adverse events)

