10.2 Adverse Event Monitoring

Monitoring adverse events will be primarily performed in two ways: 1) unsolicited report from study interventionists (physical therapist, dietitian, and meditation teacher); and 2) weekly assessments by telephone using a standardized checklist.

- Unsolicited reporting: Any adverse events that occur during the in-person or virtual sessions will be assessed for severity by the study interventionists (in conjunction

with PI or an MD co-investigator). In the event of a serious adverse event, the participant or caregiver will be instructed to contact emergency medical services to receive immediate medical attention. All adverse events will be reported to the PI.

- Standardized assessment: At the beginning of cognitive behavioral intervention telephone calls, co-investigator [name] will assess adverse events using a standardized checklist that includes the following expected adverse events (see below).

Expected Adverse Events

- Exercise: fall or injury (expected risk is low); new or worsening musculoskeletal pain (expected risk is moderate); cardiovascular events including angina, arrhythmia, myocardial infarction, heart failure, or stroke (expected risk is very low); other symptoms including chest pain, dizziness/lightheadedness, dyspnea, palpitation, or syncope (expected risk is low).
- Nutrition: gastrointestinal distress such as diarrhea, nausea, constipation (expected risk is moderate); electrolyte imbalance or dehydration (expected risk is low), renal injury from increased renal solute load (expected risk is very low)³⁸ Meditation: psychological distress (expected risk is very low/rare)³⁹
- Outcome measurement: possibility of incidental finding (such as suicidal ideation) through the Patient-Reported Outcomes Measurement Information System (PROMIS) surveys (expected risk is very low)

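### No baseline record is planned for the gastrointestinal and cardiorespiratory checklist symptoms, so symptoms that predate the program may be counted in the single-arm adverse-event proportion

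*Combined protocol and SAP*

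**What the plan says.** **Ascertainment.** Section 10.2 collects adverse events from interventionists' reports and from "weekly assessments by telephone using a standardized checklist". The checklist is given "At the beginning of cognitive behavioral intervention telephone calls". Those calls are part of the program (section 7.4), and nothing places one before the first session or the first supplement. The Overview describes the weekly calls in similar terms: "They will be asked about any potential adverse events (such as sore muscles or falls".

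**Items.** The expected events that section 10.2 says the checklist includes are not all framed alike. Musculoskeletal pain is limited to pain that is new or getting worse. The gastrointestinal item reads "gastrointestinal distress such as diarrhea, nausea, constipation (expected risk is moderate" and the cardiorespiratory item reads "other symptoms including chest pain, dizziness/lightheadedness, dyspnea, palpitation, or syncope". Neither carries that limit.

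**Baseline.** Under section 6.1, "trained research personnel will administer additional measurements that are not collected as part of preoperative assessment". The list that follows covers walking speed, chair stands, grip strength, diet recall and PROMIS. Section 6.2 extracts comorbidities, function, cognition, physical performance and nutritional status from the record. In Table 5 the adverse-event row is marked before surgery, with hospitalization as a fallback, and has no baseline mark.

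**Outcome and population.** Section 8.2 defines the outcome as the "proportion of patients who experience any adverse events per self-report". Section 10.1 defines an adverse event by its association in time with the intervention, whether or not it is judged related. On surgery type, section 5.1 requires: "Patient is scheduled to have a gastrointestinal, gynecological oncologic, urologic, and cardiovascular procedure". Under section 7 every participant receives the program.

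**The concern.** Bowel symptoms, nausea, chest pain, breathlessness and dizziness may come from the disease for which the patient is having surgery. If such a symptom is first asked about in week 1 of the program, the data hold no earlier record to compare it with. With no control arm, the participant's own state before the program is the only available comparator for these items, and the plan does not record it.

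What is at stake is how the tolerability result is read. The pilot is meant to refine the intervention for a randomized trial. A proportion that mixes effects of exercise and supplements with symptoms of the surgical disease would make the program look less well tolerated than it is. The supplement is the most exposed component, because gastrointestinal distress is its main expected effect and many participants will be having gastrointestinal surgery.

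**Working it through.** **Step 1: is there a plan figure to reproduce?** The documents give no adverse-event rate and no baseline symptom prevalence. The only plan figure used here is the target of 30 participants (section 11.1). It is consistent with its own justification: at the anticipated 70%, 21/30 has an exact 95% interval of 0.506 to 0.853, so the lower limit is just above 0.50 and the lower arm is 0.70 − 0.506 = 0.194. That figure concerns feasibility and serves below only as a denominator.

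**Step 2: which checklist items have a baseline counterpart?**

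| Checklist content (10.2) | Limited to new or worse? | Baseline record planned? |
|---|---|---|
| Musculoskeletal pain | Yes | PROMIS pain |
| Falls, injury | Not needed: an incident event | Not needed |
| Psychological distress | No | PROMIS anxiety and depression |
| Gastrointestinal symptoms | No | None |
| Cardiorespiratory symptoms | No | None |

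The gap is confined to the last two rows. Nothing in the plan links PROMIS to adverse-event classification, but for pain and mood a baseline value at least exists.

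**Step 3: direction.** Let q be the share with a truly new event, b the share with a pre-existing checklist symptom, and s the share of those pre-existing symptoms that are counted. Assuming independence:

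observed = 1 − (1 − q)(1 − b·s), so observed − q = (1 − q)·b·s ≥ 0.

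By this route the bias is upward or zero.

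**Step 4: illustrative size.** All of q, b and s are assumptions. With q = 0.30 (9 of 30):

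| b | Half counted (s = 0.5) | Of 30 | All counted (s = 1) | Of 30 |
|---|---|---|---|---|
| 0.10 | 1 − 0.70 × 0.95 = 0.335 | 10.1 | 1 − 0.70 × 0.90 = 0.37 | 11.1 |
| 0.20 | 1 − 0.70 × 0.90 = 0.37 | 11.1 | 1 − 0.70 × 0.80 = 0.44 | 13.2 |
| 0.40 | 1 − 0.70 × 0.80 = 0.44 | 13.2 | 1 − 0.70 × 0.60 = 0.58 | 17.4 |
| 0.60 | 1 − 0.70 × 0.70 = 0.51 | 15.3 | 1 − 0.70 × 0.40 = 0.72 | 21.6 |

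With q = 0.20 (6 of 30) and b = 0.30, the observed share is 1 − 0.80 × 0.85 = 0.32 to 1 − 0.80 × 0.70 = 0.44, or 9.6 to 13.2 of 30.

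**Step 5: scale and sensitivity.** The exact 95% interval for 9/30 is 0.147 to 0.494. Values up to 0.44 lie within the sampling uncertainty of a study this small; 0.51, 0.58 and 0.72 lie above it. If questioning on the call removed every old symptom (s = 0), the observed share would stay at 0.30. If old symptoms fell as far as possible on the same patients who have new events, the observed share would be the larger of q and b·s. With q = 0.30, nothing would then be added until b·s exceeded 0.30.

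**The case against.** The strongest reply is that section 10.1 already deals with this. An adverse event must be associated in time with the intervention, and an unchanged long-standing symptom is not. The attribution scale also turns on timing: it refers to the onset of the event and to a reasonable sequence from the start of study procedures. The checklist is given by a co-investigator in a live individual call, where onset can be asked. The form itself is not reproduced, so it may already contain an onset question.

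Much of this stands. A reader might infer that old and new symptoms cannot be told apart, but the documents do not support that. What they show is that the plan schedules no baseline symptom data with which to apply the timing condition, states no onset rule in section 8.2, and has no rule for symptoms present before the program. Separation would rest on recall during the program.

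A reader might also infer that no checklist symptom has any baseline measure. That is too broad. PROMIS covers pain, fatigue, anxiety and depression at baseline, and musculoskeletal pain is limited to new or worse pain. The two examples in the Overview, sore muscles and falls, are therefore not where the problem lies. A study clinician also verifies the medical history with the patient (section 6), and section 12.2 checks earlier supplement tolerance for some participants. Neither step is described as recording current gastrointestinal or cardiorespiratory symptoms.

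**Conclusion.** The point holds for the gastrointestinal and cardiorespiratory items. Symptoms that predate the program may enter the any-adverse-event proportion, with no baseline record and no control arm to show how many. Any bias by this route is upward.

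The size is unknown. The ranges of 34-51% with half counted and 37-72% with all counted rest on an assumed 30% with new events, independence, and an assumed prevalence of 10-60%. The top of the range needs the highest prevalence and no filtering by onset at all. It would be wrong to say that the documents show the proportion to be inflated, or by how much.

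A reader might infer that the decision to proceed to a trial is affected. It is not directly. Adverse events are a secondary outcome, section 11.1 plans no testing, and none of the four progression criteria in section 12.4 uses them. The planned trial against usual care would also supply the comparator that is missing here. The effect is on the pilot's safety description. The change is worth making because it is cheap and because a participant's state before the program cannot be measured later.

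**What to change.** - **Section 6.1 and Table 5:** add one administration of the section 10.2 checklist after consent and before the first session and first supplement, graded on the section 10.1 scale. Add a baseline mark to the adverse-event row.
- **Section 8.2:** count a checklist symptom only if it was absent at baseline or is worse in grade than at baseline, and add any other new event.
- **Reporting:** tabulate unchanged pre-existing symptoms separately, and show the counted events by the section 10.1 attribution categories.
- **Safety:** leave all recording and reporting of adverse events as it is. The change concerns only what enters the section 8.2 proportion.

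The cost is a few more minutes for each participant within a baseline contact that already takes place, plus wording in two sections and one table. One limitation is that, with three severity grades, a worsening within a grade will not count toward the proportion, although it stays in the safety record.

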3. STUDY OBJECTIVES

The **objective** of this pilot study is to evaluate feasibility of a prehabilitation program in frail older adults undergoing major surgery. Our **central hypothesis** is that optimizing risk factors before surgery with a multicomponent prehabilitation protocol will improve postoperative outcomes in high-risk older adults undergoing major elective abdominal, gynecological oncologic, and urologic surgery. By utilizing a patient-centered multicomponent protocol, the most effective intervention strategies of the protocol can be refined for a larger-scale randomized controlled trial. This research has four (4) intervention components: 1) physical therapy; 2) nutrition; 3) meditation; and 4) cognitive behavioral strategies will additionally be utilized to enhance motivation and support self-efficacy. We will accomplish the following two (2) **specific aims**:

3.1 Objective/Aim 1. To evaluate the feasibility of and adherence to the prehabilitation program. We will estimate the duration of preoperative geriatric assessment screening; enrollment rate; feasibility of and adherence to the prehabilitation program; attrition rate; and extent of missing outcome data. We expect that we *will be able to deliver our prehabilitation program to $\geq 50\%$ of patients*.

Feasibility is defined by proportions of enrollment, refusal, and adherence to intervention components as a whole and individually, potential barriers to adherence, and self-reported and objective measures of adherence including diaries, wearable sensors, and physical performance tests. As secondary outcomes, we will collect clinical outcomes (e.g., Postoperative Quality of Recovery Scale, surgical complications, and length of stay) and Patient-Reported Outcomes Measurement Information System (PROMIS) measures.

3.2 Objective/Aim 2. To identify barriers and facilitators of prehabilitation program and refine protocol accordingly. After the prehabilitation program, we will interview patients and their caregivers to identify facilitators, barriers, and areas for improvement. After completing all qualitative interviews, we will refine the intervention components based on participant feedback. This information will inform the design of a future, larger RCT which will target frailty using the most effective intervention components.

By completing this research, we hope to generate evidence that rehabilitation interventions are feasible and effective for optimizing risk factors before surgery. Based on our review of literature, we concluded that the success of an RCT would depend on having a feasible and acceptable prehabilitation program in the preoperative period. Therefore, we chose to focus on intervention refinement to provide necessary information to design a large RCT to compare a multicomponent prehabilitation program versus usual care on clinical and patient-centered outcomes among high risk older adults undergoing major elective surgery.

